1.3 PROTOCOL SYNOPSIS

TITLE: Combination Therapy with the Proteasome Inhibitor

Carfilzomib for the Antibody-Mediated Rejection Diagnosis in

Lung Transplantation Trial (PICARD-Lung)

Protocol number: PRO15010152

Study drug: Carfilzomib (Kyprolis®)

Phase: phase II

Patient enrollment: 30

Indication: Antibody mediated rejection after lung transplantation

Sponsor: [name]

DATE: 09/20/2018

Objectives

1: To test the hypothesis in a prospective interventional clinical trial that addition of carfilzomib to conventional therapy will result in depletion of the immunodominant DSA.

- 2: To test the hypothesis in a prospective interventional clinical trial that addition of carfilzomib to conventional therapy will result in improved or stabilized allograft function.
- 3: To test the hypothesis that lung transplant recipients with AMR have effector B cell/plasma cell populations that can be identified and characterized, and that carfilzomib alters these immune mechanisms.

Study design

Phase II, prospective, open-label, single-arm active treatment, single center pilot clinical trial of the addition of carfilzomib to conventional therapy for AMR after lung transplantation.

Outcome measures

Primary endpoint: absolute change in DSA strength, titer, and complement fixation from day 1 to day 42.

Secondary endpoints:

Absolute change in DSA strength, titer, and complement fixation from day 1 to day 90 and from day 42 to day 90

Absolute change in forced expiratory volume in 1 second (FEV1) from day 1 to day 42 and to day 90.

Presence or absence of pathologic changes consistent with AMR on transbronchial biopsy from day 1 to day 42.

Patient death at any time after day 1 attributable to AMR.

Safety endpoints:

Non-lung irreversible end-organ failure (e.g., end-stage renal disease) any time after day 1 attributable to carfilzomib.

Incidence of adverse effects (AE) requiring dose-modification any time during days 1-16.

Incidence of any AE at any time after day 1 as graded by the NIH Common Terminology Criteria for Adverse Events (CTCAE) (appendix B) criteria.

Incidence of hypogammaglobulinemia any time after day 1.

Incidence of culture-proven *de novo* infection any time after day 1.

Diagnosis of systemic inflammatory response syndrome (SIRS) any time during days 1-16

Patient death at any time after day 1 to day 90 attributable to carfilzomib.

Retrospective control group:

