4.4.2 Secondary endpoints

Secondary endpoints of this study include the following:

- 4.4.2.1 Absolute change in DSA strength, titer, and complement fixation from day 1 to day 90 and from day 42 to day 90. DSA strength will be determined by Luminex single-antigen bead testing in the neat serum and quantitated in units of mean fluorescent intensity. DSA titer will be determined by Luminex single-antigen bead testing in the diluted serum to 1:16 and quantitated in units of mean fluorescent intensity. DSA complement fixation will be determined by C1q-based Luminex single-antigen bead testing in the neat serum and quantitated in units of mean fluorescent intensity.
- 4.4.2.2 Absolute change in forced expiratory volume in 1 second (FEV1) from day 1 to day 42 and to day 90. FEV1 will be quantitated via UPMC PFT lab standard methods on routine pulmonary function testing obtained in the routine clinical care of these patients.
- 4.4.2.3 Presence or absence of pathologic changes consistent with AMR on transbronchial biopsy from day 1 to day 42. Pathologic changes consistent with AMR will be defined as follows: Complement-4d fixation on >50% (diffuse) of the capillaries in the biopsy by standard immunoperoxidase method, capillaritis by standard hematoxylin and eosin (H&E) stain; or endothelialitis by standard H&E stain.
- 4.4.2.4 Patient death at any time after day 1 attributable to AMR.
- A 1:1 retrospective control group including lung transplant recipients from the University of Pittsburgh with Antibody Mediated Rejection will be created to describe differences in the endpoints using the CFZ-based regimen vs. historic standard of care.

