4.4.3 Safety outcomes

Safety outcomes of the study include the following:

- 4.4.3.1 Non-lung irreversible end-organ failure (e.g., end-stage renal disease) any time after day 1 attributable to carfilzomib.
- 4.4.3.2 Incidence of adverse effects (AE) requiring dose-modification (see section 5.3.1.2) any time during days 1-16.
- 4.4.3.3 Incidence of any AE at any time after day 1 as graded by the NIH Common Terminology Criteria for Adverse Events (CTCAE) (appendix B) criteria, as follows:
 - Grade 1: Mild; asymptomatic or mild symptoms; clinical or diagnostic observations only; intervention not indicated.
 - Grade 2: Moderate; minimal, local or noninvasive intervention indicated; limiting ageappropriate instrumental ADL (Instrumental ADL refer to preparing meals, shopping for groceries or clothes, using the telephone, managing money, etc.).
 - Grade 3: Severe or medically significant but not immediately life-threatening; hospitalization or prolongation of hospitalization indicated; disabling; limiting self-care ADL (self-care ADL refer to bathing, dressing and undressing, feeding self, using the toilet, taking medications, and not bedridden).
 - Grade 4: Life-threatening consequences; urgent intervention indicated.

Grade 5: Death related to AE.

- 4.4.3.4 Incidence of hypogammaglobulinemia any time after day 1.
- 4.4.3.5 Incidence of culture-proven *de novo* infection any time after day 1.
- 4.4.3.6 Diagnosis of systemic inflammatory response syndrome (SIRS) any time during days 1-16; requiring at least 2 of the following 4 criteria:

Body temperature: < 36 or > 38 degrees Celsius

Tachycardia: > 90 beats per minute

Tachypnea: > 20 breaths per minute

White blood cells: < 4000 or > 12000 cells/mm³

- 4.4.3.7 Patient death at any time after day 1 attributable to carfilzomib.
- A 1:1 retrospective control group including lung transplant recipients from the University of Pittsburgh with Antibody Mediated Rejection will be created to describe differences in the endpoints using the CFZ-based regimen vs. historic standard of care.

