5.4 Study assessments

See appendix B for full listing of study data collection.

Study therapy will be given as an inpatient. Screening patients for AMR as defined above in section 4.3 for enrollment in the trial may occur as an inpatient or outpatient. Patients will undergo a minimum 16 day hospitalization for conventional AMR therapy and for study carfilzomib. Patients may return to the clinic for standard of care visits on days 28 and 42 and 90 (2 and 4 and 10 weeks post therapy completion) for assessment as described below.

Patients will be followed in the study until day 90. There are no follow-up visits as part of this research study, however, if patients return to their standard of care routine visits, a medical record review will be performed to obtain this data from patients' medical records, whenever available. Patients will be subsequently followed by their treating physician under routine clinical care for recurrent AMR until they expire and any available clinical information related to their standard lung transplant care will be obtained from medical records up to 360 days.

For patients who prematurely discontinue therapy, all future planned study and routine clinical care assessments will be completed unless the patient expires. An assessment for the purpose for premature discontinuation will be taken at the time of study discontinuation.

The University of Pittsburgh laboratories will be used to assess all samples. DSA samples will be processed by the University of Pittsburgh Histocompatibility Lab under the direction of co-investigator [name]. PBMC isolation, and exploratory testing samples will be process by the research lab of co-principal investigator [name].

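### Three of the seven safety outcomes are zero in the retrospective controls by definition, and AMR-attributed death has no common end day or attribution rule, so the control comparison cannot answer the safety question as written

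*Combined protocol and SAP*

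**What the plan says.** Sections 4.4.2 and 4.4.3 each close with the same statement. It introduces "A 1:1 retrospective control group including lung transplant recipients from the University of Pittsburgh with Antibody Mediated Rejection" and says that this group "will be created to describe differences in the endpoints using the CFZ-based regimen vs. historic standard of care". Neither section exempts any endpoint.

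The outcomes at issue are:

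- 4.4.3.1: irreversible failure of an organ other than the lung, attributed to carfilzomib, with no closing day.
- 4.4.3.2: "Incidence of adverse effects (AE) requiring dose-modification (see section 5.3.1.2) any time during days 1-16". Section 5.3.1.2 confines dose changes to events judged related to the study drug.
- 4.4.3.7: "Patient death at any time after day 1 attributable to carfilzomib". The synopsis (1.3) words the same outcome as "Patient death at any time after day 1 to day 90 attributable to carfilzomib".
- 4.4.2.4: "Patient death at any time after day 1 attributable to AMR".

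For trial patients, Section 5.4 ends study follow-up at day 90, after which clinical information "will be obtained from medical records up to 360 days". Appendix A describes that review as running to one year. For controls, the public text gives no index day, follow-up limit or rule for cause of death. Section 5.13 reserves Kaplan-Meier for displaying the treated patients, not for comparing them with another group, and names no other method for the control comparison.

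**The concern.** The control group is the only place where the trial could show whether death or organ failure is more frequent when carfilzomib is added. There are three obstacles, and better matching of controls removes none of them.

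- **Fixed zeros.** An outcome that requires carfilzomib exposure cannot occur in a control. A control who reaches end-stage renal disease after plasma exchange and IVIG does not count under 4.4.3.1.
- **One-sided attribution.** Investigators judge causality to carfilzomib themselves (6.2.3) in an open-label trial. A treated patient's death can leave the AMR category by being assigned to the drug. A control's death cannot.
- **No common end day.** Outcomes with no closing day are limited to about a year in the trial arm by other sections, but nothing limits them in controls. Without a time-to-event comparison, crude proportions would carry any difference in follow-up.

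Section 3.1 expects the trial to establish the safety and efficacy of the combination, and Section 4.1 intends it to inform larger controlled trials. A difference fixed by definition, or produced by unequal follow-up, would mislead both uses.

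**Working it through.** **Group size.** Section 5.13.3: 10 patients per year × 3 years = 30, matching the enrolment in 4.1. At 1:1 this gives 30 controls. The plan states no event rate, effect size or power, so there is no further figure to reproduce.

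**Which outcomes can occur in a control?** Of the seven safety outcomes, 4.4.3.1, 4.4.3.2 and 4.4.3.7 cannot. The other four (4.4.3.3 any AE, 4.4.3.4 hypogammaglobulinemia, 4.4.3.5 culture-proven infection, 4.4.3.6 SIRS) can. So 3 of 7 are fixed at 0/30. If the true rate of such an outcome in treated patients is 5% or 10% (assumed), the chance of at least one event in 30, and hence of a difference to describe, is 1 − 0.95^30 = 0.785 or 1 − 0.90^30 = 0.958.

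**Which outcomes have no closing day?** 4.4.2.4, 4.4.3.1, 4.4.3.3, 4.4.3.4, 4.4.3.5 and 4.4.3.7. That is 6 of the 12 listed endpoints (1 primary, 4 secondary, 7 safety).

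**Effect of unequal windows on AMR death, with no true effect.** Assume the same constant hazard in both groups and a risk p at day 360. Cumulative risk by day t is 1 − (1 − p)^(t/360). The documents give neither p nor the control window; both are my assumptions.

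| p | day 90 | day 360 | day 720 | day 1080 |
|---|---|---|---|---|
| 10% | 2.6% | 10% | 19.0% | 27.1% |
| 20% | 5.4% | 20% | 36.0% | 48.8% |
| 30% | 8.5% | 30% | 51.0% | 65.7% |

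With the trial arm counted to day 360:

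- Controls to day 1080: an apparent benefit of 17 to 36 points. At p = 20% this is 6.0 against 14.6 expected deaths in 30.
- Controls to day 360: a difference of 0.
- Controls to day 90: the sign reverses, by 7 to 21 points against carfilzomib.

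**Effect of attribution, with equal windows.** If a share f of treated AMR deaths is assigned to carfilzomib instead, the treated rate reads p(1 − f). At p = 20% and f = 10% to 30%, treated reads 18% to 14% against 20%. Over p = 10% to 30% the gap runs from 1 point (0.10 × 0.10) to 9 points (0.30 × 0.30). In counts: with 6/30 deaths in each group and two treated deaths relabelled, AMR death reads 4/30 (13.3%) against 6/30 (20.0%), a gap of 6.7 points with equal total mortality.

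The opposite error is also possible. If retrospective records miss AMR as the cause in 10% to 30% of control AMR deaths, controls at p = 20% read 18% to 14%, which equals or falls below the 18% in treated patients at f = 10%.

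**End day of carfilzomib death.** The synopsis stops at day 90; 4.4.3.7 does not stop. The two cannot both be applied.

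**The case against.** A reader might infer that AMR death is certain to be biased toward carfilzomib, even with perfect matching. The documents do not support that.

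- No control follow-up length is stated, so longer control records are a supposition. A rule fixing an index day and cut-off for controls would remove the window effect entirely.
- Section 6.3.4 lets AMR progression and study therapy each be noted as a contributing factor. One death may carry both, and the relabelling example assumes an either/or choice that the text does not impose.
- If the two relabelled deaths really were caused by the drug, AMR deaths really were fewer.

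A reader might also infer that the comparison can show nothing about harm. That goes too far. Infection, any AE by grade, hypogammaglobulinemia and SIRS need no attribution to carfilzomib, and 6.3.4 records all deaths irrespective of cause.

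Finally, the stated purpose is only descriptive, no test is planned, and a zero for carfilzomib death in patients never given carfilzomib is easily recognised.

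Most of this stands. It makes the direction and size of the bias conditional. It does not remove the fixed zeros, supply a common window, or say how a death with both notations counts under 4.4.2.4. A truly drug-related death that replaces an AMR death is no gain to the patient, so an AMR-only count misleads there as well. Being descriptive lowers the stakes but does not make the described difference informative.

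**Conclusion.** The point holds in this form. It is certain from the definitions that three of the seven safety outcomes are 0/30 in controls, and that the synopsis and 4.4.3.7 disagree on the end day. It is also clear that AMR-attributed death and five safety outcomes lack an end day shared with controls, and that only treated deaths can be assigned to carfilzomib. The comparison is therefore open to bias. It probably favours carfilzomib if controls are counted beyond day 360, disappears on the window side if windows are equal, and reverses if control windows are shorter.

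The figures (a window gap of 17 to 36 points at day 360 against day 1080; an attribution gap of 1 to 9 points) rest on assumed risks, windows and relabelling shares. They illustrate size and are not forecasts. The change is worth making before any control records are abstracted.

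**What to change.** In 4.4.2, 4.4.3 and 5.13:

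1. For every statement that sets the trial arm beside the controls, use all-cause death, any new irreversible non-lung organ failure regardless of attribution, and the existing culture-proven infection outcome (4.4.3.5).
2. Count all three from day 1 (a defined index day in controls) to day 90, with all-cause death also to day 360. Truncate control records at the same days.
3. Report 4.4.3.1, 4.4.3.2, 4.4.3.7 and AMR-attributed death descriptively, for the trial arm only.
4. Reconcile the end day of carfilzomib-attributed death between the synopsis and 4.4.3.7.

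The cost is mainly wording. All-cause outcomes are less specific to AMR or to carfilzomib, and control data need chart abstraction over the stated window. Small additions are also needed in the trial arm. Appendix B collects death only to day 90 and has no item for organ failure regardless of cause, and 6.2.1 limits SAE recording after the reporting period to drug-related events. The record review to day 360 should therefore state that every death is captured. No extra patients, visits or treatment changes are needed.

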6.1.2 Adverse effect (AE) definition

An AE is any unfavorable and unintended sign, symptom, or disease temporarily associated with the use of an investigational medicinal product or other protocol-imposed intervention, regardless of attribution.

This includes the following:

AEs not previously observed in the patient that emerge during carfilzomib therapy (days 1through 16, and 28, 42, 90), including signs or symptoms associated with AMR that were not present prior to the AE reporting period.

Complications that occur as a result of protocol-mandated interventions.

AEs that occur prior to the assignment of study treatment that are related to a protocol-mandated intervention.

Preexisting conditions judged by the investigators to have worsened in severity or frequency or changed in character during carfilzomib therapy (days 1through 16, and 28, 42, 90).

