6.2.2 Eliciting adverse events

A consistent methodology of non-directive questioning for eliciting AEs at all patient evaluation time points will be adopted.

This will include the following two questions directed to study subjects:

How have you felt since your last infusion of carfilzomib?

Have you had any new or changed health problems since you were last seen?

These questions will be asked in person at days 28, 42 and 90 ±14 days, or by phone if patient does not return to their standard of care visit at these time points.

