9.1 Appendix A: Study Flowcharts

Study Procedures								In		enti ±14 d	on Pl lays	hase							Festin Phase	e		Po	st-stu	dy Fo
	0	1	2	3	4	5	6	7	8	9	10	11	12	13	14	15	16	28	42	90	120	150	180	210
Screening/Enrollment	х																							
Standard of Care Procedure	es.																							
H&P		Х																						
Progress note			Х	Х	Х	Х	Х	Х	Х	Х	х	Х	Х	Х	Х	х	х	Х	Х	Х	Х	Х	Х	Х
PLEX 1.5 volumes		Х		Х		Х		Х		Х		Х		Х		Х								
Premeds for IVIG		Х		Х		Х		Х		Х		Х		Х		Х	Х							
IVIG 100 mg/kg		Х		Х		Х		Х		Х		Х		х										
IVIG 500 mg/kg																Х	Χ*							
Medrol 750-1000 mg IV		Х	Х	Х	on	ly gi	ven	if co	ncor	nita	nt AC	îR												
CBC w/differential		Х	Х	Х	Х	Х	Х	Х	Х	Х	х	Х	х	х	Х	Х	Х	Х	Х	Х	Х	Х	Х	
CMP		Х	Х	Х	Х	Х	Х	Х	Х	Х	х	Х	Х	Х	Х	Х	Х	Х	Х	Х	Х	Х	Х	
Total IgG		Х															Х	Х	Х	Х	Х	Х	Х	
Complement 3 & 4		Х															Х	Х	Х	Х			Х	
Luminex IgG-SAB		Х															Х	х	Х	Х	Х	Х	Х	Х
Luminex C1q-SAB		Х															х	Х	Х	Х	Х	Х	Х	Х
PFTs		Х																Х	Х	Х	Х	Х	Х	Х
TB Biopsy		Х																	Х					clin
Study Specific Procedures																								
Premeds for CFZ		Х	Х						Х	Х						Х	Х							
CFZ 20 mg/m2		Х	Х						Х	Х						Х	Х							
CFZ AE assess			Х	Х	Х	Х	Х	Х	Х	Х	х	Х	Х	Х	Х	Х	Х	Х	Х	Х				
CFZ response assess																		х	х	х				
IgG-SAB subclasses**		Х															х	х	х	х				
Blood for PBMC**		Х															х	Х	Х	Х				

Progress notes indicate inpatient admission or clinic visits within ±14 days of the stated days, unless the patient is unable to present due to unforeseen circumstances (e.g., death, hospitalization at another facility, etc.). Standard of care procedures will not be done solely for research purposes.

Study ends at the day 90 visit. Post-study follow-up will continue for all patients alive at day 90 to 1 year post enrollment through a medical records review.

Study CFZ AE assessment will be conducted either in-person or via telephone (day 1 through 16, and 28, 42 and 90

^{*} Dose will be administered only If IgG level is below 700 mg/dL.

^{**} Research samples will only be obtained if subject is coming to their standard of care visit on days 28, 42 and 90.

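### The any-AE contrast with retrospective controls (4.4.3.3) is confounded by ascertainment: events are actively elicited in carfilzomib patients and cannot be in controls

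*Combined protocol and SAP*

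**What the plan says.** **The comparison.** Section 4.4.3 lists seven safety outcomes and ends with a 1:1 retrospective control group that "will be created to describe differences in the endpoints using the CFZ-based regimen vs. historic standard of care". No outcome is exempted. Outcome 4.4.3.3 is "Incidence of any AE at any time after day 1 as graded by the NIH Common Terminology Criteria", and counting starts at grade 1: "Mild; asymptomatic or mild symptoms; clinical or diagnostic observations only; intervention not indicated".

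**Carfilzomib patients.** Section 6.2.2 states: "A consistent methodology of non-directive questioning for eliciting AEs at all patient evaluation time points will be adopted". It scripts two questions, one of which asks about the last carfilzomib infusion. They are put in person around days 28, 42 and 90, "or by phone if patient does not return to their standard of care visit at these time points". The Appendix A footnote adds: "Study CFZ AE assessment will be conducted either in-person or via telephone", and covers the treatment days as well. Under 6.2.3 and 6.3 the investigators assess severity and causality, and each event goes on its own AE form.

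**Controls.** The protocol gives no data source, index day, observation window or grading method. The definition in 6.1.2 begins: "An AE is any unfavorable and unintended sign, symptom, or disease temporarily associated with the use of an investigational medicinal product", and extends to other interventions imposed by the protocol.

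**Analysis.** Section 5.13.2 lists AEs by patient, cycle and dose and summarises them by event, system and grade. Section 5.13 says the Kaplan-Meier curves are not for comparing groups. No method is given for the between-group safety description that 4.4.3 promises.

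**The concern.** A difference in AE incidence has a meaning only if an event of a given kind has about the same chance of being recorded in each group. Here one group is asked repeatedly, and phoned if a visit is missed. The other can contribute only what was already on record. Mild symptoms that lead to no intervention are counted in 4.4.3.3 and are the events most likely to go unrecorded unless someone asks. Outcome 4.4.3.3 carries no attribution to carfilzomib, so it looks comparable across groups when it is not.

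No hypothesis test or decision rule uses the contrast, so what is at stake is a misleading description. Section 3.1 says completion of the aims will establish the safety as well as the efficacy of the combination. A reader would naturally take an AE excess over historical care as toxicity added by carfilzomib.

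**Working it through.** **1. Group sizes.** Section 5.13.3: 10 patients per year x 3 years = 30, which reproduces the planned enrolment. The 1:1 ratio implies 30 controls. No AE rate, AE difference, alpha or power is stated.

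**2. Scheduled AE contacts, carfilzomib group.** The Appendix A grid marks days 2-16 plus 28, 42 and 90: 15 + 3 = 18. Its footnote and Appendix B start at day 1: 16 + 3 = 19. For controls nothing is stated.

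**3. Spurious difference when carfilzomib adds no AEs.** Let p be the true any-AE risk in both groups, and s_T and s_C the probabilities that a patient's AE is captured among treated patients and controls. Then

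observed difference = p x (s_T - s_C), and observed risk ratio = s_T / s_C.

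All three inputs are assumptions: p = 0.5 to 0.9, s_T = 0.95, s_C = 0.8 to 0.4.

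| p | s_C = 0.8 | s_C = 0.6 | s_C = 0.4 |
|---|---|---|---|
| 0.5 | 7.5 points | 17.5 points | 27.5 points |
| 0.7 | 10.5 points | 24.5 points | 38.5 points |
| 0.9 | 13.5 points | 31.5 points | 49.5 points |
| Risk ratio | 1.19 | 1.58 | about 2.4 |

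For example, 0.7 x (0.95 - 0.6) = 0.245. With 30 per group the 95% half-width there is 1.96 x sqrt(0.665 x 0.335/30 + 0.42 x 0.58/30) = 0.244. Across the table it is about 20 to 25 points, so the bias can equal or exceed the sampling error. Equal capture gives a spurious difference of 0.

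**4. If carfilzomib does add AEs.** With true risks 0.7 vs 0.5 and capture 0.95 vs 0.6, the observed difference is 0.665 - 0.300 = 0.365 against a true 0.200. The artefact share is 0.165/0.365 = 45%. Over true risks of 0.7 vs 0.5, 0.9 vs 0.7 and 0.9 vs 0.5, with the same capture range, the share runs from 12% to 65%.

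**5. Several events per patient.** If each patient has K true events, each captured independently with probability s, then P(at least one recorded) = 1 - (1 - s)^K and the mean recorded count is K x s. At capture 0.95 vs 0.6:

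- K = 1: 95% vs 60%.
- K = 2: 99.7% vs 84%.
- K = 5: 100% vs 99%, but mean counts of 4.75 vs 3.0.

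The patient-level proportion saturates. Counts, and summaries by event and grade, do not.

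**6. Which events are exposed.** Of the rows in the 6.1.4 table with all-grade frequency of at least 10% (32 rows, summing to 641.0 percentage points), 18 are symptoms, summing to 355.2 (55%). Their grade 3-and-above frequencies sum to 25.1, so grade 1-2 symptoms are (355.2 - 25.1)/641.0 = 51.5%. This describes reports in earlier carfilzomib trials. It is not an estimate of the AE mix, or of losses, in controls.

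**7. Hypogammaglobulinemia (4.4.3.4), a separate mechanism.** The outcome is IgG below 700 mg/dL at any time, so incidence rises with the number of tests. With probability q of a low result per test and k independent tests, incidence is 1 - (1 - q)^k. At an assumed q = 0.2, the four scheduled post-baseline tests give 59%; an assumed two control tests give 36%. Independence makes this an upper illustration. Positive correlation between a patient's tests narrows the gap, to zero at the extreme.

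**The case against.** The strongest reply is that control records may be better than the word retrospective suggests. Conventional therapy requires an inpatient stay, and Appendix A lists daily progress notes, blood counts and metabolic panels as standard of care. If controls were treated the same way, days 1-16 could be densely documented. Section 6.3.3 limits laboratory AEs to those needing active management, which a chart can show. Symptoms such as dyspnea, cough, diarrhea and vomiting (102.6 of the 355.2 points above) would plausibly be noted in such patients. This stands as a reason why the gap may be modest to day 16. It does not replace the questioning and calls at days 28, 42 and 90, and the protocol does not say that controls had this care or how their records would be used.

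Several stronger readings are tempting but not supported:

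- A reader might infer that the AE difference is driven by ascertainment. Capture rates and true risks are not stated, the artefact share falls well below 100% if there is a real effect, and the any-AE proportion can saturate.
- A reader might infer that controls have nothing but chart notes. The control data source is never described.
- A reader might take the by-group summaries in 5.13.1 as a plan to contrast AEs. That wording covers baseline characteristics and study-drug administration only.
- A reader might infer that the contrast would feed the planning of later trials. Section 4.1 names the rate of response as the information needed for that.
- A reader might extend the AE argument to IgG. That is a question of test frequency. Section 5.4.1 calls total IgG a research procedure, drawn at days 28, 42 and 90 only if the patient attends a routine visit, while Appendix A lists it as standard of care. The number of tests is therefore uncertain in both groups.

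**Conclusion.** The point holds in this form: the planned description of differences in 4.4.3.3 is confounded by ascertainment and not interpretable. The protocol states the contrast and the active elicitation in carfilzomib patients. Retrospective controls cannot be elicited in that way, and nothing in the plan equalises capture. The definition in 6.1.2, tied to an investigational product or protocol-imposed intervention, leaves it unclear what would count as an AE in a control.

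The likely direction is more apparent harm with carfilzomib, strongest for grade 1-2 symptomatic events and for event counts. The size cannot be fixed from the documents. The 7.5 to 49.5 points rest on equal true risk and assumed capture probabilities, and shrink toward zero for the any-AE proportion if most patients have several events. The primary endpoint is not affected. The hypogammaglobulinemia point is secondary. The change is worth making because it is cheap and removes a contrast that the control data cannot support.

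**What to change.** In 4.4.3, replace the blanket control sentence with three statements:

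1. AE-form data (4.4.3.3) are reported for the carfilzomib group only and are not contrasted with controls.
2. Any between-group description of harm is limited to events abstracted from the medical record with the same form in both groups. It runs from a defined index day (start of AMR therapy) over the same window, and does not use AE forms or study phone contacts in the carfilzomib group. All-cause death and positive clinical cultures are suitable examples. Culture results also depend on how often cultures are taken, so show the number per patient.
3. If hypogammaglobulinemia is compared, use a common time point instead of an any-time incidence, show the number of IgG tests per patient, and note possible selection among those tested.

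While the sentence is open, also exclude outcomes 4.4.3.1, 4.4.3.2 and 4.4.3.7 from the contrast. They require attribution to carfilzomib or a dose modification and so cannot occur in controls. That is a separate fault of the same sentence.

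Cost: protocol wording, one abstraction form, and staff time to apply it to about 60 records (30 + 30). No visits or tests are added. The loss is any between-group contrast for low-grade symptomatic AEs.
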